Due to recruitment setbacks related to COVID-19, some samples and data previously collected from another study, Cardiovascular Effects of GLP-1 Receptor Activation (P.I., Dr. [name] (Vanderbilt University Medical Center (VUMC) IRB# 170213, ClinicalTrials.gov Identifier: NCT03101930) will be included to help meet our enrollment goals for the obese subject population. In this prior study (VUMC IRB# 170213), obese individuals underwent the same study procedures that we are performing in the present study as outlined below (subcutaneous adipose tissue biopsy, indirect calorimetry, DXA body composition scan), and thus the samples/data have already been collected. These samples were of similar inclusion criteria as the currently recruiting study, with the minor adjustment of age criteria of up to 65 years of age. For the prior study (VUMC IRB#170213), subjects signed a consent form which indicated their consent for their samples/data to be used for future research. Samples provided from this study will be de-identified for our use. There are approximately 122 obese individuals from this prior study with available baseline samples/data relevant to any of our endpoints, of whom approximately 80 individuals have adipose biopsy data (our primary endpoint). The inclusion of these samples will enable us to analyze baseline data for approximately 105 obese subjects with adipose biopsy data (primary endpoint) (from the subjects that we are able to personally recruit, as well as the previously collected samples/data from the prior study).

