#### 10.0 Statistical Considerations

Sample size justification: A total of 100 subjects will provide 80% power to detect a minimum difference between lean and obese groups of 0.7 units of UCP1 mRNA expression normalized for housekeeping gene mRNA gene expression (primary analysis). This represents a metabolically meaningful difference of approximately 0.45 standard deviations between lean and obese groups. These calculations are based on a Type 1 error rate of 0.05, and interindividual variations in UCP1 gene expression reported in prior studies. Since there is only 1 main study visit, dropouts should not be an issue in this study. However, there is a low likelihood that some adipose tissue samples may be inadequate quantity or quality. Even if some adipose tissue samples are of insufficient quantity or quality, a sample size of 80 would still provide 80% power to detect a minimum difference between groups of 0.75 units in UCP1 normalized mRNA expression, which represents a metabolically meaningful difference of approximately 0.48 standard deviations between lean and obese groups.

Of note, the above sample size calculation was based on the original enrollment goal of 100 subjects. Now that we have the benefit of including some samples from a previously completed study, our statistical power to answer our scientific questions will be improved.

Statistical Analysis: The primary analysis will determine whether adipose tissue gene expression of UCP1 differs between lean and obese individuals. To assess this, we will use multivariable linear regression, with UCP1 gene expression as the outcome variable, and BMI as the independent variable. The multivariable linear regression will be adjusted for covariates that may impact markers of beige adipose tissue, including age and sex. The null hypothesis is that UCP1 gene expression will not differ based on BMI. Secondary analyses include whether UCP1 gene expression differs by race and whether expression of additional "beiging" markers differ by obesity status. Like the primary analysis, the secondary analyses are analyzing a continuous outcome variable. Thus, the statistical approach for the secondary analyses will be similar to that described for the primary analysis.

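### The 0.45 and 0.48 SD power figures do not reproduce, and the claimed gain from borrowed samples is not quantified for the 50:105 design and depends on the two studies being exchangeable

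*Combined protocol and SAP*

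**What the plan says.** The sample size paragraph of Section 10.0 states: "A total of 100 subjects will provide 80% power to detect a minimum difference between lean and obese groups of 0.7 units" of normalised UCP1 mRNA, described as a "metabolically meaningful difference of approximately 0.45 standard deviations between lean and obese groups". For the case where some biopsies are unusable it adds that "a sample size of 80 would still provide 80% power to detect a minimum difference between groups of 0.75 units", or "approximately 0.48 standard deviations between lean and obese groups". On error control it says only: "These calculations are based on a Type 1 error rate of 0.05". It gives no sidedness, no lean:obese split for the 100, and no assumed variance explained by covariates.

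The next paragraph notes that this calculation belongs to the former enrolment goal of 100 and says that, with prior-study samples added, "our statistical power to answer our scientific questions will be improved". No calculation follows for the enlarged sample.

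Section 2.0 (Aim 1) and Section 4.0 give the current target as about 50 lean and 105 obese. Section 5.0 explains that the borrowed samples come from an earlier study of obese people, "of whom approximately 80 individuals have adipose biopsy data", and that the combined total will be "approximately 105 obese subjects with adipose biopsy data (primary endpoint"). The primary model in Section 10.0 is a linear regression of UCP1 expression on BMI, adjusted for covariates that include age and sex. It names no term for study of origin.

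**The concern.** A reader of Section 10.0 will take away that the study had 80% power at 0.45 SD and now has more. Two things stand in the way.

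First, the starting figure looks too favourable for 100 subjects. If so, the enlarged sample could be a genuine improvement and still fall short of the power on the page.

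Second, every borrowed subject is obese. The lean group is not enlarged, and study of origin becomes strongly associated with obesity status: 80/105 = 76% of the obese group, and none of the lean group, come from the earlier study. Without a source term, about three quarters of any between-study shift in measured UCP1 would pass into the lean-obese difference. Checking for such a shift means using the concurrent subjects, who are far fewer than 155. The extra power is therefore conditional on an assumption that the plan neither states nor tests.

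**Working it through.** **Inputs.** From Section 10.0: alpha 0.05, power 80%, 0.7 units = 0.45 SD at N = 100, 0.75 units = 0.48 SD at N = 80. From Sections 2.0, 4.0 and 5.0: 50 lean, 105 obese, about 80 of the obese borrowed; hence about 105 − 80 = 25 newly recruited obese. Assumed, because not stated: 50:50 and 40:40 splits for the earlier totals (equal allocation is the most favourable), equal SDs, and a two-sided test, with one-sided shown alongside.

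**Formula.** Detectable difference in SD units ≈ (z_alpha + z_power) × √(1/n1 + 1/n2). The multiplier is 1.960 + 0.842 = 2.802 two-sided and 1.645 + 0.842 = 2.486 one-sided. The tabulated values use the noncentral t, which is slightly larger.

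**Step 1: the plan's own figures.**
- Implied SD: 0.7/0.45 = 1.556 and 0.75/0.48 = 1.563 units, so the unit and SD figures agree with each other.
- N = 100: 2.802 × √(1/50 + 1/50) = 2.802 × 0.200 = 0.560; noncentral t 0.566. The plan says 0.45.
- N = 80: 2.802 × √(1/40 + 1/40) = 2.802 × 0.2236 = 0.626; noncentral t 0.634. The plan says 0.48.
- One-sided: 0.501 and 0.561, so neither value is recovered that way.
- Subjects needed for 0.45 SD, two-sided at 1:1: 2 × 2.802²/0.45² = 77.5, so 78 per group and 156 in all (124 one-sided).
- Internal scaling: 0.45 × √(100/80) = 0.503, not 0.48.
- Covariate R² that would rescue the figures: 1 − (0.45/0.560)² = 0.355 at N = 100; 1 − (0.48/0.626)² = 0.413 at N = 80.

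**Step 2: the current and concurrent samples.** For 50:105, √(1/50 + 1/105) = 0.1718. The balanced equivalent is 4 × 50 × 105/155 = 135 subjects. For 50:25, √(1/50 + 1/25) = 0.2449, equivalent to 4 × 50 × 25/75 = 67 subjects.

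| Comparison | Detectable, two-sided | Power at 0.45 SD, two-sided | Detectable, one-sided | Power at 0.45 SD, one-sided |
|---|---|---|---|---|
| 50:50 | 0.566 SD | 61% | 0.501 SD | 72% |
| 50:105, source ignored | 0.484 SD | 74% | 0.429 SD | 83% |
| 50:25, concurrent or source-adjusted | 0.695 SD | 44% | 0.615 SD | 57% |

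At 1.556 units per SD, the two-sided values for 50:105 and 50:25 are 0.75 and 1.08 units. Both terms in 105 − 80 are approximate: with 20 to 35 newly recruited obese subjects, the two-sided concurrent figure runs from 0.752 to 0.625 SD.

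**Step 3: why a source term reduces the contrast to 50:25.** With a lean/obese indicator and a source indicator, the prior-study subjects are all obese. They determine the source coefficient and nothing else, so the obesity coefficient rests on the concurrent subjects.

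**Step 4: BMI entered as a continuous variable.** BMI variation within the prior study then still informs the slope. Information is proportional to the BMI sum of squares, taken within source if a source term is fitted. The documents give no BMI distribution; assume lean mean 22 (SD 1.7), and an obese mean of 35 to 40 with SD 4 to 8 in both studies. Example with obese mean 38, SD 6:
- 50:50: 25 × 16² + 50 × 1.7² + 50 × 6² = 8,344.5.
- 50:105 without a source term: (50 × 105/155) × 16² + 50 × 1.7² + 105 × 6² ≈ 12,596, ratio 1.51.
- 50:105 with a source term: (50 × 25/75) × 16² + 50 × 1.7² + 105 × 6² ≈ 8,191, ratio 0.98.

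Over the assumed range the ratio is 1.42 to 1.66 without a source term and 0.80 to 1.28 with one.

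**The case against.** A reader might infer that the sentence promising improved power is false. The documents do not support that. Under the model as written, with no source term, power does rise like for like: 61% to 74% at 0.45 SD. The shortfall against 0.45 SD arises because that figure was too favourable for 100 subjects. If covariates did explain the 36% of variance that would make it true, 50:105 would detect 0.481 × 0.45/0.560 = 0.39 SD. One-sided, 50:105 reaches 0.43 SD without any such help. All of this stands, and it limits the shortfall to a two-sided, unadjusted comparison.

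A reader might also infer that any source term leaves the study weaker than it was originally. That is too broad. The plan specifies no source term, the split of the original 100 is not given, and the 50:25 reduction applies to a binary lean/obese contrast. Section 10.0 poses the question as lean versus obese but names BMI as the independent variable; with BMI continuous, the information could be lower or higher than in the 50:50 design.

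Three further points count for the sponsor. Section 5.0 says the prior study used the same procedures and similar eligibility apart from a higher age limit (65 against 55), and age is a covariate; this supports comparability without establishing it. Borrowing followed recruitment setbacks, so without it the study might have had about 50:25 anyway; borrowing did not cause that loss. And the sentence refers to the scientific questions in general: the Aim 2 associations across about 155 participants may well gain. None of this supplies the missing calculation or the exchangeability condition.

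**Conclusion.** The point holds in this form. The stated 0.45 SD (N = 100) and 0.48 SD (N = 80) are not reproduced by a two-group comparison at 0.05, one- or two-sided; the two-sided values are about 0.57 and 0.63 SD. Only an unstated covariate R² of roughly 36% to 41% would recover them. The 50:105 sample is a real improvement on the recomputed baseline, to 0.48 SD, but two-sided and unadjusted it gives 74% rather than 80% power at 0.45 SD.

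That improvement is conditional on exchangeability of the two studies. For a lean-versus-obese contrast, separating source from obesity leaves about 50:25 and 0.70 SD, which is weaker than 50:50 on either sidedness and across 20 to 35 newly recruited obese subjects. For a continuous BMI slope the direction is not determined by the documents. The conclusion rests on the assumed equal splits for the earlier totals, equal SDs, and 25 as the difference of two approximate counts. The confounding of source with obesity does not depend on those assumptions, and the plan does not address it.

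**What to change.** In Section 10.0, replace the 0.45 and 0.48 SD figures and the statement of improved power with figures for the actual design. On a two-sided 0.05 test at 80% power these are about 0.48 SD for 50:105 if the studies are exchangeable, and about 0.70 SD for the concurrent lean-obese comparison (about 50:25). State the sidedness, the allocation, and any covariate R² relied on, with its source. Say whether BMI enters as lean/obese or as a continuous variable, since that decides what a source term costs.

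Report a concurrent-only or source-adjusted estimate beside the pooled primary estimate, and state that the pooled estimate assumes no between-study difference in UCP1 beyond the covariates.

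The cost is a rewording of Section 10.0 and one additional model on data the study will already hold. No further enrolment is required. The stated power becomes less favourable, and the concurrent estimate will be imprecise.

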# 11.0 Privacy/Confidentiality Issues

Strict confidentiality will fully be maintained possible by the research team, including keeping all data in a secure location. All specimens will be de-identified and coded after they are obtained, and the code key kept in a secure location. Only study personnel will access to the data and specimens. Samples may be shared with third parties outside of the VA and Vanderbilt for future testing but will remain anonymous to the recipient. Subjects may contact the principal investigator at any time to request that samples be destroyed. However, any data or biological samples that have already been used for research cannot be destroyed.

The Research Electronic Data Capture (REDCap) database is a secure web application housed on the TVHS VA secured computer network and is password protected. REDCap offers secure institutional data hosting and includes full audit-trails in compliance with HIPAA security requirements. Only members of the study team will have access to this database.

Adverse event reports and annual summaries will not include subject-identifiable material but only the assigned study identification numbers.

#### 12.0 Follow-up and Record Retention

Anticipated study duration is 40 months. Research data will be maintained by the PI after study closure. After study closure, research data will be maintained for a minimum of 6 years and possibly indefinitely. Data will be stored on a secure computer network in a password-protected database. Only members of the study team will have access. Pertinent paper documentation will be kept in locked office and only study personnel will have access. Only personnel directly involved with the study will have access to source data and the electronic database.

VA Tennessee Valley Healthcare System, [name]

